2.2 Study Objectives and Endpoints

Primary Objectives:

Acceptability and Tolerability

- To evaluate the acceptability and tolerability of each study product when applied rectally and used prior to RAI
 - Placebo rectal insert
 - Placebo rectal douche
 - Placebo rectal suppository

Adherence

- To evaluate adherence to each study product prior to RAI over a 4-week-long period
 - Placebo rectal insert
 - Placebo rectal douche
 - Placebo rectal suppository

Exploratory Objective:

Relative Acceptability and Tolerability

- To evaluate the relative acceptability and tolerability between study products when applied rectally and used prior to RAI
 - Placebo rectal insert
 - Placebo rectal douche
 - Placebo rectal suppository

Primary Endpoints:

Acceptability and Tolerability

- For each study product, participant self-report of likelihood of product use if shown to be effective

Adherence

- Per participant report, percentage of occasions when each study product was used as instructed (per protocol)

Safety

- Grade 2 or higher related adverse events (AEs) as defined by the Division of AIDS Table for Grading the Severity of Adult and Pediatric Adverse Events, Corrected Version 2.1, July 2017, and/or Addenda 1, 2 and 3 (Female Genital [Dated November 2007], Male Genital [Dated November 2007] and Rectal [Clarification Dated May 2012] Grading Tables for Use in Microbicide Studies)

Exploratory Endpoint:

Relative Acceptability and Tolerability

- Conjoint analysis of participant acceptability and tolerability between the three study products

2.3 Randomization

Participants will be randomly assigned with the ratio 1:1:1:1:1:1 to one of six study product application sequences. The randomized assignments will be in blocks to keep the balance of equal allocation.

2.4 Blinding

Participants and site staff will be unblinded throughout the trial due to this study being an open label trial.

2.5 Sample Size and Power

There is no control group for comparison in this study. The goal is not to compare each product to some standard but instead to estimate overall rates of acceptability, adherence and safety.

Primary Endpoints – Acceptability/Tolerability and Adherence

Based on previous studies we expect to observe a high rate of acceptability (>80%) which equates to $\leq 20\%$ of participants reporting a low likelihood of using the product in the future (≤ 3 on the rating scale). Likewise, we expect to observe a high rate of participants reporting taking at least 90% of expected doses.

The table below shows the exact confidence intervals for acceptability and adherence, assuming $\alpha=0.05$ based on the Binomial distribution and varying rates of acceptability and adherence. The power to rule out <50% and <70% acceptability or adherence given the rates is also shown. Calculations assume the outcomes are observed in 200 of the participants (5% loss to follow-up). For example, if the true acceptability or adherence rate is 90%, we have 100% power to rule out a true acceptability or adherence rate of 75% or lower. If we observe an 80% acceptability or adherence rate, the corresponding 95% confidence interval (CI) will be (74%, 85%).

Table 2: Exact 2-sided 95% Confidence Intervals Based on Various Rates of Acceptability or Adherence Endpoints

Acceptability rate / adherence rate	95% CI if rate is observed	Power to rule out 50% if rate is true	Power to rule out 70% if rate is true	Power to rule out 75% if rate is true
95%	(91, 98)	100%	100%	100%
90%	(85, 94)	100%	100%	100%
85%	(79, 90)	100%	100%	93%
80%	(74, 85)	100%	90%	35%

Primary Endpoint – Safety

To characterize the statistical properties of the safety endpoint, the table below presents the probability of observing zero, at least one, and two or more safety endpoints among 200 participants (allowing for the possibility of 5% dropout) assuming various “true” event rates. By assuming that we may only have safety evaluations on 200 participants, these calculations are conservative. However, safety analyses will include all enrolled participants.

Table 3: Analysis of Safety Event Frequency

Event Rate	P(0 events n=200)	P(≥ 1 event n=200)	P(≥ 5 events n=200)	P(≥ 10 events n=200)
0.1%	82%	18%	0%	0%
0.5%	37%	63%	0%	0%
1%	13%	87%	5%	0%
2%	2%	98%	37%	1%
5%	0%	100%	97%	55%

3. GENERAL DATA ANALYSIS CONSIDERATIONS

3.1 Analysis Set(s)

Safety endpoints will be assessed on a modified intent-to-treat analysis set, which will include all participants enrolled in the study who received at least one of the study products during the study. Primary acceptability, tolerability and adherence endpoints will be assessed on a per-protocol (PP) analysis subset, which will consist of participants who received all three study products and completed the corresponding product use end visits (PUEVs).

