## **10.7 Data Analyses**

### **10.7.1 Primary Analyses on Acceptability/Tolerability and Adherence Measures**

All primary analyses will be based on data from the participants with data in all three periods of study (participants who complete each period of the study). Baseline values between these participants and those participants lost to follow-up will be described and used to interpret the generalizability of the results. Additionally, secondary analyses will analyze endpoints among all participants. The adherence and acceptability/tolerability endpoints (defined in Section 10.3.1) will be reported with 95% CI. The purpose of this protocol is not to compare the placebo products; therefore, we do not plan on doing comparisons between products in the primary analysis. Logistic regression models will be used to assess the order of product use (period effect) on acceptability/tolerance and adherence.

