2. INTRODUCTION

This SAP is intended to describe the final primary and secondary analyses upon completion of MTN-035.

[figure not shown]

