6.2 Treatment Exposure

The number and percentage of participants who received each of the three study products, along with the number and percentage of participants who completed the corresponding product use end visit (PUEV) will be displayed in a table overall and by site, and in a table overall and by randomized sequence. In addition, the number and percentage of participants who received all three study products and completed all three PUEV will also be displayed.

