8. PRIMARY ENDPOINTS

The acceptability, tolerability and adherence primary endpoints will be evaluated on the per-protocol subset of participants, i.e. participants who received all three study products and completed the corresponding PUEV, and thus provide relevant data from all three periods of study. Assessment of these endpoints will be based on responses from the participants to the computer assisted self-interviews (CASI) at the three PUEVs (Visits 3, 5 and 7). To aid in the interpretation of the resulting analyses, baseline characteristics of the per-protocol subset of participants including, but not limited to, study site, sequence, sex/gender, and age will be described and compared to those of participants who were lost to follow-up.

Acceptability and Tolerability

The acceptability and tolerability endpoint will be based on question H1 of the CASI:

“Think about the positive and negative experiences you have had using the rectal Insert during the past 4 week period. If this rectal insert was available and it provided some protection against HIV, how likely would you be to use it before receptive anal sex?”.

Responses to this question for each product were captured from visual Likert scale from 1 (very unlikely) to 10 (very likely). Participants’ responses corresponding to the three product use periods will be displayed in tables by study product, by study product and site and by study product and randomization sequence.

To compare acceptability and tolerability between study products, the endpoint will be operationalized as binary, with scores 1 to 6 grouped as “low acceptability” and scores 7 – 10 as “high acceptability”. Number and percentage of participants giving a “high acceptability” score will be display in tables by study product, with exact binomial 95% confidence intervals (Clopper-Pearson method).

Adherence

Two endpoints related to adherence will be assessed: adherence to use per-protocol and adherence to use per-anal-sex-act. These are defined as follows:

1. **Adherence to use per-protocol:** Number and proportion of participants who reported not having missed a rectal [enema/douche, insert or suppository] application in the previous 4 weeks, according to the participants’ response to question B0 of the CASI:

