B0. The following questions refer to your use of the study provided rectal [**study product: douche/enema, insert or suppository**] over the past 4 weeks. You were asked to insert the study provided rectal [**study product**] in your rectum at least once a week during the past 4 weeks. However, for different reasons, people might have encountered difficulties using the [**study product**]. Thinking about your experience during these past four weeks, in how many of the weeks did you miss a rectal [**study product**] application?

- 0 weeks
- 1 week
- 2 weeks
- 3 weeks
- 4 weeks

Responses to question B0 will be tabulated by study product, study product and sequence and study product and site, along with the number and proportion of participants fully adherent (those

who reported 0 weeks missing application), with 95% confidence intervals (Clopper- Pearson). If needed, additional categories of invalid/missing responses will be included.

- 2. Adherence per sex-act:** Proportion of times when participants reported having used the study-provided rectal douche/enema, insert or suppository before receptive anal sex. For participants who reported at least 1 anal sex act in the previous 4 weeks, this proportion will be obtained by dividing the number reported in Question B2 over the number reported in Question B1 of the CASI:

B1. How many times did a partner put a penis in your rectum during the past 4 weeks?

B2. Of those [] times, how many times did you use the study-provided rectal **[study product: douche/enema, insert or suppository]** BEFORE receptive anal sex? (If you did not use the douche prior to anal sex, please enter '0'.)

Responses to Questions B1 and B2 will be cross tabulated, by study product and by study product and site. If needed, additional categories of invalid/missing responses will be included. Summary statistics (mean and SD, median and IQR) of participants' per sex-act adherence, as defined above, will be displayed by study product and by study product and site.

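### The SAP leaves out the all-participant secondary analysis of acceptability and adherence that the protocol promises, so valid ratings of one product drop out of that product's rate

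*SAP*

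**What the plan says.** Protocol 10.7.1 makes two commitments in one paragraph. On the primary set: "All primary analyses will be based on data from the participants with data in all three periods of study". On the secondary set: "Additionally, secondary analyses will analyze endpoints among all participants". The second carries no condition on the amount of missing data.

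SAP section 2 gives its own scope: "This SAP is intended to describe the final primary and secondary analyses upon completion of MTN-035". SAP 3.1 then defines two sets. The modified intent-to-treat set is for safety. The per-protocol set is for acceptability, tolerability and adherence, "which will consist of participants who received all three study products and completed the corresponding product use end visits (PUEVs". SAP section 8 applies it again: these endpoints "will be evaluated on the per-protocol subset of participants, i.e. participants who received all three study products and completed the corresponding PUEV".

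The SAP also plans some description of participant loss. Section 8 says that baseline characteristics of the per-protocol participants "will be described and compared to those of participants who were lost to follow-up". Section 6.1 tabulates retention and reasons for stopping. Section 6.2 counts receipt of each product, "along with the number and percentage of participants who completed the corresponding product use end visit (PUEV". SAP 3.2 starts sensitivity analyses and multiple imputation only above 10% missing and otherwise uses the available data. Protocol 10.8 has the same threshold.

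**The concern.** Acceptability (question H1) and adherence (B0, and B1 with B2) are asked separately for each product, by computer self-interview at Visits 3, 5 and 7. Each primary estimate concerns one product and needs only that product's visit. The completer rule goes further: a missed visit for one product removes the participant's answers about the other two.

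Protocol 7.5.3 gives a concrete route. A participant who stops by their own choice in the third period is terminated from the study. If that happens before Visit 7, the answers already given at Visits 3 and 5, about two other products, do not enter the section 8 rates.

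The protocol accepted the completer set as primary but paired it with an all-participant analysis, which would show whether a product's completer rate also holds among everyone who rated it. If the SAP is followed as written, that second set of rates is not produced. The planned baseline comparisons and visit counts describe who left, but not how those people rated the products they had used.

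**Working it through.** **1. Which analysis appears where**

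| Analysis of acceptability and adherence | Protocol | SAP |
|---|---|---|
| Rates in three-period completers | 10.7.1, primary | 3.1 and 8 |
| Endpoints among all participants | 10.7.1, secondary, unconditional | none specified |
| Sensitivity analysis above 10% missing | 10.8 | 3.2 |
| Mixed models between products | not the same (10.7.1 has logistic models for order of use) | 10, exploratory, analysis set unstated, odds ratios |

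Only the second row is lost between the two documents.

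**2. The plan's own figures**

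Inputs from SAP 2.5: 210 enrolled, 200 evaluable, two-sided exact 95% intervals. The Clopper-Pearson limits for x of n are the 2.5% quantile of Beta(x, n−x+1) and the 97.5% quantile of Beta(x+1, n−x).

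- 160/200 = 80.0%, interval 73.8 to 85.3. SAP Table 2 states 74 to 85, so it reproduces.
- Power to rule out 70% at a true 80%: the lower limit exceeds 70% from 153 of 200 upward, and P(X ≥ 153) = 90.6%. The table states 90%.

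The sample-size arithmetic is sound. Lost precision is also a minor matter: with 189 completers the same power is 88.7%.

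**3. How many ratings can go unused**

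Let m be the number of non-completers. A non-completer has at most two valid end-visit responses, so at most 2m ratings are unused, or 2m/3 per product if spread evenly. The lower limit is zero, when no non-completer has a valid response.

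- Planned 5% loss: m = 210 − 200 = 10, at most 20 unused ratings, 20/3 ≈ 7 per product. Raters per product: 200 + 7 = 207.
- 10% loss: m = 210 × 0.10 = 21, completers 189, at most 42 unused ratings, 42/3 = 14 per product. Raters per product: 189 + 14 = 203.

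**4. What the omitted analysis could show at that upper limit**

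Assumption: about 80% of completers rate the product highly (160/200, or 151/189 = 79.9%). The documents give nothing on the excluded participants, so their rate is varied from 0% to 100%.

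| Scenario | Unused ratings that are high | Rate among all raters | 95% interval |
|---|---|---|---|
| 5% loss | none of 7 | 160/207 = 77.3% | 71.0 to 82.8 |
| 5% loss | all 7 | 167/207 = 80.7% | 74.6 to 85.8 |
| 10% loss | none of 14 | 151/203 = 74.4% | 67.8 to 80.2 |
| 10% loss | 7 of 14 | 158/203 = 77.8% | 71.5 to 83.3 |
| 10% loss | all 14 | 165/203 = 81.3% | 75.2 to 86.4 |

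For comparison, the completer interval at 10% loss is 73.5 to 85.4 (151/189), which excludes the 70% benchmark of SAP Table 2. In the least favourable row the all-raters interval does not. At 5% loss even the least favourable row excludes 70%.

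**The case against.** Several points on the other side stand.

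- **The 10% trigger.** A reader might infer that the SAP is at fault for planning no missing-data sensitivity analysis at or below 10%. The documents do not support that. The threshold is the protocol's own, in 10.8, and SAP 3.2 repeats it. The departure is only the dropped all-participant analysis.
- **The section 10 models.** A reader might also infer that partial data are never used. That is too strong. SAP 3.1 restricts the primary endpoints to the per-protocol set, and section 10 carries no such restriction. A model with a participant random intercept can use people with one or two ratings, and SAP 3.2 speaks of available data. But the set is unstated, and the output is an odds ratio between products. SAP 2.5 says the aim is to estimate rates. What is missing is a rate for each product.
- **Selective loss.** It is narrower than it may look. The per-protocol set requires receipt of the products and completed end visits, not continued use. Someone who dislikes a product and stops using it stays in the set if all three end visits are completed, and protocol 7.5.3 lets those who stop by choice in periods 1 or 2 go on to the remaining products.
- **Wording of the promise.** The protocol's sentence is short and does not say how participants without a rating are handled. Reading it as everyone with a valid response for that product is reasonable, but it is an interpretation.
- **Outer bounds.** It is tempting to size the problem by counting every non-completer as a low or a high rating. If non-completers gave no rating, the omitted analysis would equal the completer analysis, so such bounds do not measure this omission. Neither document promises them.

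**Conclusion.** The point holds as a mismatch between protocol and SAP. The protocol promises an all-participant secondary analysis, the SAP claims to cover secondary analyses, and no such rate is specified. The completer primary set is what the protocol asks for and is not an error.

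The possible size is modest at the planned 5% loss, at most a fall of 80.0 − 77.3 = 2.7 percentage points or a rise of 0.7. At 10% it reaches a fall of 79.9 − 74.4 = 5.5 points or a rise of 1.4. These figures assume about 80% in completers, exactly one missed end visit per non-completer, an even spread over products, and unused ratings that are all low or all high. If half are high at 10% loss, the fall is 79.9 − 77.8 = 2.1 points. With fewer unused ratings the range narrows, down to no change at all.

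A reader might infer that the completer rates are biased upward. The documents do not show this, and the direction is unknown. The primary result stands. What is missing is a promised check on it, which should be set out in the SAP and not left to a choice after the data are seen.

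**What to change.** Keep the completer set as primary.

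1. Add to SAP 3.1 and 8, for each product, a secondary analysis of everyone who received that product and gave a valid H1, B0 or B1/B2 response at its end visit. State that this is how the protocol's reference to all participants is read.
2. Report high acceptability and full adherence on B0 with Clopper-Pearson intervals, and per-sex-act adherence with the statistics already planned ("Summary statistics (mean and SD, median and IQR"), each beside the completer result.
3. State in SAP section 10 that the mixed models for acceptability and adherence use this same set of available ratings.

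The cost is SAP wording and one extra table per endpoint, from data already collected. Denominators will differ slightly between products, and the estimates may be less favourable than the completer rates. No study procedure changes.

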### 7.5.3 Participants Who Permanently Discontinue Study Product for Other Reasons

For participants who permanently discontinue use of one of the study products for any clinician-initiated reason, the PSRT should be consulted regarding continued study participation and progression to other study products. For participants terminated from the study after PSRT consult, an Early Termination Visit will be conducted, if the participant is willing. See [Section 9](#) for additional details regarding clinical follow-up of AEs unresolved at the time of study termination.

Participants who permanently discontinue use of one of the study products for any self-initiated reason during the first or second product use period will be allowed to continue in the study and progress to the other study product(s), if they are willing. Participants who permanently discontinue study product use for any self-initiated reason during the

third product use period will be terminated from the study, and an Early Termination Visit will be conducted, if the participant is willing. See [Section 9.8](#) for additional details.

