## **7.8 Behavioral Evaluations**

All participants will respond to computer assisted self-interviews (CASI) at the Enrollment Visit (Visit 2) and at the three PUEVs (Visits 3, 5 and 7), and to a conjoint analysis assessment at the Final Visit (Visit 8). The assessment done at enrollment will include, among other topics, questions on participants' prior experiences and comfort using rectal products, as well as douching or other rectal hygiene practices. The follow-up

assessments will explore reactions to each study product and administration method, including participants' perceptions of their partners' reactions. These assessments will allow investigators to identify product attributes likely to challenge and/or facilitate future sustained use when applied rectally by participants. Suggestions for product improvement will also be collected. The conjoint analysis assessment will compare between the three study products, including questions on participant preferences regarding the different formulations.

Participants will also complete a brief weekly report of product use via SMS/IM for each study product. A brief IDI is planned for all participants at the three PUEVs (Visits 3, 5 and 7). These IDIs will review and explore participants' responses to acceptability, tolerability, and adherence questions asked via SMS/IM during each product use period.

Based on Behavioral Research Working Group (BRWG) review of SMS/IM data, approximately 10 participants per site will be selected and invited to complete a longer IDI at the Final Visit (Visit 8). This IDI will include questions comparing user acceptability of the study products, user-centered suggestions for product design and delivery, acceptability and factors influencing product use, douching history and education, and experiences with the application methods, among other topics. Suggestions for product improvement will also be collected. The audio from the IDI will be recorded and transcribed for analysis. The interview notes, recording and transcript will be considered as source documentation.

Major components of both CASI and IDI assessments have been used successfully and validated in prior rectal microbicide trials (e.g., MTN-006, MTN-007, MTN-017) and are being implemented/planned as part of MTN-026, MTN-033 and MTN-037.

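### Primary acceptability and adherence rates use three-PUEV completers only; quitters of the third product normally drop out, full adherence (B0) is slightly inflated, and the SAP omits the promised all-participant analysis

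*SAP*

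**What the plan says.** **Analysis set.** Protocol 10.7.1: "All primary analyses will be based on data from the participants with data in all three periods of study". SAP 3.1 defines the set as those "which will consist of participants who received all three study products and completed the corresponding product use end visits (PUEVs"), and SAP 8 repeats it: "participants who received all three study products and completed the corresponding PUEV, and thus provide relevant data from all three periods of study".

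**Stopping a product by choice.** Under protocol 7.5.3, someone who stops in period 1 or 2 "will be allowed to continue in the study and progress to the other study product(s), if they are willing". Someone who stops in the "third product use period will be terminated from the study, and an Early Termination Visit will be conducted, if the participant is willing".

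**Where the endpoint data come from.** SAP 8 takes acceptability (H1) and adherence (B0, B1, B2) from the CASI at Visits 3, 5 and 7. Protocol 7.8 schedules "computer assisted self-interviews (CASI) at the Enrollment Visit (Visit 2) and at the three PUEVs (Visits 3, 5 and 7"). For Visit 8, protocol 7.4.3 and 7.8 name only the conjoint assessment for all participants, plus an interview in a subset. Protocol Table 8 lists a generic behavioral assessment there.

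**Adherence endpoint.** B0 asks "in how many of the weeks did you miss a rectal" application. Full adherence means an answer of zero weeks.

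**Other analyses.** Protocol 10.7.1 adds: "Additionally, secondary analyses will analyze endpoints among all participants". SAP 3.2 plans sensitivity analyses and multiple imputation, assuming ignorable missing data, only when more than 10% is missing. SAP 8 also compares the baseline characteristics of completers with those of participants lost to follow-up.

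**The concern.** Protocol 10.3 and SAP 2.5 say the aim is to estimate rates, so the per-product rate is the main result. Quitting a product is direct evidence about adherence to it. Yet a voluntary stop in period 3 normally means no third PUEV, and the participant then leaves the primary rate for every product. Two things follow.

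- Valid CASI answers for the first and second products are set aside for a reason unrelated to those products.
- A person who stopped before the last weekly dose missed at least one week and cannot be fully adherent on B0. That known failure leaves the denominator when it should count against the rate.

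The same loss affects anyone taken off all products under protocol 9.3 in period 1 or 2, and a period 1 or 2 stopper who is unwilling to go on. It does not affect a period 1 or 2 stopper who continues and attends every PUEV, or anyone who misses doses but attends.

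**Working it through.** **Inputs.** 210 enrolled, 35 per sequence (SAP Table 1). 200 analysed after 5% loss, with exact 95% intervals (SAP 2.5). The missing-data trigger is more than 10%, so up to 21 of 210 can be lost without reaching it (SAP 3.2). Each product comes third in 2 of 6 sequences, so 2 × 35 = 70 participants use it in period 3. The documents give no number of voluntary stoppers; every stopper count below is an assumption.

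**The plan's own figures.** Clopper-Pearson for 160/200 gives 73.8% to 85.3%; SAP Table 2 prints (74, 85). At a true 80%, power to rule out 70% is 90.6% (printed 90%), and power to rule out 75% is 33.5% (printed 35%). The table reproduces to within 2 points. The half-width at 80% is (85.3 − 73.8)/2 ≈ 5.8 points.

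**Bias in the B0 rate for one product.** Let k be the number lost, n = 210 − k, m the number of those k who stopped this product by choice and so are not fully adherent, and p the true rate in all 210. The other k − m are assumed adherent with probability p. Then

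expected reported rate r = [210p − (k − m)p]/n = p(n + m)/n,

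so each stopper adds p/n. At p = 0.80 and n = 200 this is 0.80/200 = 0.4 points.

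The last column is the chance that the exact 95% interval lies wholly above the true 80%, taking the adherent count as binomial(n, r).

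| Lost k | Assumption about losses | m | Reported rate | Interval wholly above truth |
|---|---|---|---|---|
| 10 | no stoppers | 0 | 80.0% | 1.8% |
| 10 | half are stoppers, even over products | 1.67 | 80.7% | 3.1% |
| 10 | all are stoppers, even over products | 3.33 | 81.3% | 5.1% |
| 10 | all stopped this one product | 10 | 84.0% | – |
| 21 | half are stoppers, even | 3.5 | 81.5% | 5.2% |
| 21 | all are stoppers, even | 7 | 83.0% | 13.4% |

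**The same in terms of period 3 use.** If 2% of the 70 stop and lack Visit 7, m = 1.4 per product, k = 3 × 1.4 = 4.2, n = 205.8, and the shift is 0.80 × 1.4/205.8 = 0.5 points. If 5% stop, m = 3.5, k = 10.5, n = 199.5, and the shift is 0.80 × 3.5/199.5 = 1.4 points.

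**What counting stoppers would do to an observed 160/200.** Three stoppers give 160/203 = 78.8% (72.5 to 84.2). Five give 160/205 = 78.0% (71.7 to 83.5). Ten, the one-product extreme, give 160/210 = 76.2% (69.8 to 81.8).

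**The case against.** The strongest reply is that the completer set is a deliberate, disclosed choice. Protocol and SAP agree on it, the SAP labels it per-protocol, and completers are compared with those lost to follow-up so that generalizability can be judged. Protocol 10.7.1 also promises an all-participant analysis regardless of the missing-data rate, which would bring back the period 1 and 2 answers. This stands in part: the selection is acknowledged, and it would be wrong to say that no all-participant analysis was ever intended. But the SAP, which says it describes the final primary and secondary analyses, never specifies one for these endpoints. Comparing baselines describes the loss without correcting a rate, as do the tables of early stops and PUEV completion in SAP 6.1.3 and 6.2. The SAP 10 mixed models give odds ratios between products, not a rate per product.

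Second, the missing third-product CASI is an inference. Table 8 lists a behavioral assessment at the termination visit, using the same label as the PUEVs, and protocol 7.5.4 allows interim visits for missed procedures. Operational detail sits in a manual outside these documents. This also stands in part, and is why the point says normally. Still, no text makes the termination visit a PUEV, and it takes place only if the participant is willing.

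Third, the effect is small, and the larger figures need every loss to be a voluntary stop, whereas the plan calls its 5% loss to follow-up. This stands.

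A reader might go further and infer that acceptability or per-sex-act adherence is also biased upward. The documents do not support that. A stopper's H1 score is unknown, and the share of acts covered by product (B2/B1) need not be low. The effect on the other two products has no fixed direction either.

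**Conclusion.** The point holds in limited form. The completer restriction, combined with termination of period 3 stoppers, removes participants who are known failures on B0, so the fully adherent rate for the stopped product is expected to be biased upward. At the planned 5% loss and a true 80%, the shift is 0.7 points if half the losses are stoppers and 1.3 points if all are, spread evenly over products. The 84.0% figure is an upper bound that needs all 10 losses to be quitters of a single product; it should not be read as a forecast. With 21 lost, still short of any sensitivity analysis, the even-spread figures are 81.5% and 83.0%. Above 10%, imputation under ignorability would predict a stopper's B0 answer and not use the weeks known to be missed.

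These sizes assume that stoppers quit before the last weekly dose, lack a third PUEV, and that other losses share the true rate. The likely shift is well inside the interval half-width and changes no stated decision. The firmer defect is that the protocol's all-participant analysis has no specification in the SAP. This is a cheap improvement worth making, not a flaw that undermines the trial.

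**What to change.** In SAP 3.1 and 8, whatever the missing-data rate:

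1. Specify a per-product analysis of acceptability and adherence in every participant who received that product and has CASI data for it, shown beside the three-PUEV completer analysis. This delivers what protocol 10.7.1 promises and keeps the period 1 and 2 answers.
2. Specify a B0 sensitivity analysis in which a documented voluntary stop before the last weekly dose counts as not fully adherent. Handle other missing B0 answers under SAP 3.2.

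Counting a stop as failure changes a self-reported endpoint into a composite. That is a choice of estimand, so it belongs in a named sensitivity analysis and not in the primary definition. It does not recover H1 for the stopped product.

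**Cost.** No new visits or data collection are planned for: discontinuations go on CRFs (protocol 9), reasons are tabulated (SAP 6.1.3), and weekly SMS/IM use reports exist (protocol 7.8). That these records date the stop relative to the last weekly dose is an assumption to confirm. Denominators will differ slightly between products, and reported adherence may be slightly lower.
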